9.0 Evaluation During Study

- 9.1 A history and physical exam will be performed at two month intervals for a total of 24 months of follow up after the completion of the assigned treatment (±30 days). Note the first evaluation after radiotherapy will frequently be performed approximately 4 weeks after completion of radiotherapy and then the study will continue with history and physical exam at 2 month intervals.
- 9.2 Neuropsychological testing will be performed at each follow up visit, up to two years post radiation treatment. Reasonable effort will be made to complete this testing prior to patients meeting with their physicians and receiving information about the status of their disease.
- 9.3 Routine MR imaging of the brain performed with and without contrast will be obtained at each follow up visit at 2 month intervals (±30 days) until recurrence or up to two years post radiation treatment. Note the first evaluation after radiotherapy will frequently be performed approximately 4 weeks after completion of radiotherapy and then the study would continue with follow-up imaging at 2 month intervals. These post-treatment scans will be analyzed and compared to baseline scans for identification of regions demonstrating changes in contrast enhancement including size, heterogeneity and rim thickness. Qualitative estimation of associated T2-FLAIR changes will also be evaluated. Early stages of malignant gliomas have demonstrated decreased water diffusion. Routinely obtained diffusion weighted images and reconstructed ADC maps will be analyzed to see if there is a difference between pre- and various post-treatment scans. Based on contrast enhancing imaging features, manually selected regions of interest on ADC maps will be

quantitatively analyzed, normalized to contralateral unaffected brain parenchyma and compared on serial scans. Similarly DTI maps and cognitive functions will be correlated.

- 9.4 Medication usage (specifically steroid dose, narcotic pain medications, antiepileptic agents, psychostimulants) will be recorded. Steroid doses will be adjusted based on clinical and radiographic criteria.
- 9.5 Requirements for more frequent evaluation will be documented. Data on unscheduled follow-ups will also be documented.

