10.0 Criteria for Response and Toxicity

10.1 Definition of primary endpoint:

- 10.1.1 Time to cognitive failure on any of the 6 primary variables from the pre-specified cognitive tests (HVLT-R total recall, HVLT-R delayed recall, HVLT-R delayed recognition, TMT Part A or Part B, COWA) with failure defined as a decline that meets or exceeds the reliable change index (RCI) for each cognitive test variable. A cumulative incidence approach will be used to estimate median time to cognitive failure in order to account for the competing risks of disease progression and death. Patients experiencing disease progression or patients that died prior to experiencing cognitive failure will be considered as having had a competing event. Progressive disease frequently causes cognitive decline, and the goal of this study is to assess the impact of the radiation treatment itself on cognitive decline.
- 10.2 Definitions of secondary endpoints:
 - 10.2.1 Local control and distant control in the brain will be measured by contrast-enhanced brain MRI scan using Response Assessment in Neuro-Oncology (RANO)Criteria, as follows [50].
 - 10.2.1.1 Complete Response (CR): Requires all of the following 1) complete disappearance of all enhancing measurable and non-measurable disease sustained for a minimum of 4 weeks; 2) no new lesions; 3) stable or improving nonenhancing (T2/FLAIR) lesions; 4) patients must be off corticosteroids (or on physiologic replacement doses only); and 5) stable or improved clinically.
 - 10.2.1.2 Partial Response (PR): Requires all of the following: 1) ≥50% decrease compared with baseline in the sum of products of perpendicular diameters of all measurable enhancing lesions sustained for at least 4 weeks; 2) no progression of non-measurable disease; 3) no new lesions; 4) stable or improved non-enhancing (T2/FLAIR) lesions on the same

or lower dose of corticosteroids compared with the baseline scan; 5) stable or improved clinically.

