- 10.2.4 At each two month interval follow up visit out to 2 years all six prespecified cognitive test variables will be assessed. The pattern of cognitive change in memory, executive function, and processing speed will be assessed at each time point. The composite cognitive function

score will be determined by averaging standardized Z-scores from all pre-specified cognitive test variables (5 out of 6 are required to calculate a composite score).

- 10.2.5 MRI imaging including diffusion weighted images (DWI) and reconstructed apparent diffusion coefficient (ADC) maps will be analyzed for differences between pre- and post-treatment scans. They will also be analyzed for differences between the two treatment modalities.
- 10.2.6 Diffusion tensor imaging (DTI) will be analyzed for correlation to the cognitive changes and for differences between the two treatment modalities.
- 10.2.7 Pre-treatment factors of RPA class and MMSE will be assessed for predictive determination of local and distant control and cognitive outcome in each treatment arm.
- 10.2.8 Assessment will be made for correlation between location of primary lesion, total volume of intracranial disease, and cognitive outcome for each of the treatment arms.
- 10.2.9 The relationship between MGMT promoter methylation status and cognitive and local control outcomes will be assessed.
- 10.2.10 Post treatment side effects will be recorded at each follow up visit out to two years. Toxicity will be recorded according the Common Terminology Criteria for Adverse Events v4.0.3 for Nervous System Disorders. Only grade 3 and above toxicity that is directly related to therapy will be required to be documented. Pretreatment symptoms should not be considered as toxicity related to the treatment and are not required to be documented unless the symptoms worsen as a result of therapy.
- 10.2.11 Dosimetric parameters such as dose to the hippocampus will be analyzed for relationship with cognitive and local control outcomes.
- 10.3 Evaluation of correlative markers
 - 10.3.1 Genetic markers: DNA will be extracted within the first five fractions of treatment in the laboratory of the Study Chair. Apo E (i.e., Apo E2, Apo E3, and Apo E4) genes will be analyzed for single nucleotide polymorphisms (SNPs) either by Taqman or direct sequencing.

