We will use descriptive statistics to summarize by treatment arm the quality of life data at each assessment time. We will also use boxplots to summarize the quality of life data by treatment arm at each assessment time. We will model the quality of life data using mixed effects regression methods with repeated measures. The model will include treatment arm, selected dosimetric parameters, baseline cognitive function, location of the primary tumor (left vs. right hemisphere, if bilateral disease is present, location will be determined by the hemisphere with highest burden of disease), and the stratification factors used at randomization as fixed effects and patient as a random effect. We will similarly analyze the cognitive tests. For nearly all the prior mentioned analyses we will also plan to conduct an as-treated analysis.

We will tabulate by treatment arm the adverse events by grade and relationship to treatment.

We will use logistic regression methods to model the logit of the probability of neurocognitive decline as function of ApoE (i.e., Apo E2, Apo E3, Apo E4) genotyping, inflammatory markers (i.e., IL-1, IL-6, TNF- α), and hormone growth factors (i.e., glucocorticoids, gonadal steroids, growth hormone, human chorionic gonadotrpin, insulin-like growth factor-1, neuronal growth factor).

Determination of MCP class will be determined by RPA analysis using results of MGMT, *IDH1*, G-CIMP, and mRNA assays as well as RTOG RPA class. We will use descriptive statistics to report class distributions overall and by treatment arm. Survival by classes will be visualized on Kaplan/Meier plots, compared by the logrank test. The Cox proportional hazards regression will be used to model MCP classification, adjusting for treatment arm and stratification factors.

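### The longitudinal cognitive model in section 12.4 has no rule for scores taken after progression, so its result does not separate tumour-driven from radiation-related decline (minor; secondary analysis only)

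*Combined protocol and SAP*

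**What the plan says.** - **Aim.** Section 10.1.1 notes that progression often brings cognitive decline and adds that "the goal of this study is to assess the impact of the radiation treatment itself on cognitive decline". The primary analysis (10.1.1, 12.3) therefore treats progression and death before cognitive failure as competing events.
- **Testing schedule.** Section 9.2: "Neuropsychological testing will be performed at each follow up visit, up to two years post radiation treatment". Section 10.2.4: "At each two month interval follow up visit out to 2 years all six prespecified cognitive test variables will be assessed". Neither stops at progression. The neighbouring imaging item, 9.3, does have a stop: MRI continues "until recurrence or up to two years post radiation treatment". Section 11.0 does not remove patients at progression.
- **Model.** Section 12.4: "We will model the quality of life data using mixed effects regression methods with repeated measures". On its terms: "The model will include treatment arm, selected dosimetric parameters, baseline cognitive function, location of the primary tumor" (left or right hemisphere), "and the stratification factors used at randomization as fixed effects and patient as a random effect". For cognition it adds only "We will similarly analyze the cognitive tests".
- **Variants.** Section 12.4 repeats the secondary analyses in all patients and in evaluable patients, and plans as-treated versions of nearly all of them. These change who is analysed or how patients are grouped, not which visits count.
- **Objective.** Objective 3.2.4 asks for the pattern of cognitive change at two-month intervals over two years. It does not mention progression.

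**The concern.** The primary endpoint goes out of its way to keep tumour progression apart from cognitive failure. The longitudinal analysis of the same six test variables has no such step, although the schedule plans for scores after progression. The background in section 4.0 reports studies in which progression was the dominant cause of cognitive decline in high-grade glioma, while noting that they predate combined-modality treatment.

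What is at stake is interpretation. If tumour control differs between the arms, through treatment or by chance in a trial of 90 patients, the arm coefficient for cognition can move even when both techniques affect normal brain equally. The protocol leaves that difference open: it compares local and distant failure by arm, and sections 1.0 and 4.0 cite preclinical evidence of a greater effect of protons on tumour cells. A favourable coefficient could then be read as brain sparing when it reflects tumour control, or an imbalance could hide real sparing.

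**Working it through.** **1. The plan's own figure.** No sample size or power is given for the mixed models. The only design figure is the 43 events for the primary comparison. From 45% and 30% failure at 4 months under exponential times, HR = ln(0.70)/ln(0.55) = 0.597. Schoenfeld events at one-sided 0.20 and 80% power = 4 × (0.8416 + 0.8416)² / ln(0.597)² = 42.5, rounded up to 43. The figure reproduces, and nothing below changes it.

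**2. What the text implies.** Testing runs to 2 years, patients are not removed at progression, and the model has neither a cut-off nor a progression term. Taken together, scores after progression would enter the model. The plan does not say so in words.

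**3. Inputs for the size.**
- From the documents: 2-year survival of 27.2% with radiotherapy plus temozolomide (section 4.0); visits every 2 months to month 24.
- Assumed, not in the documents: exponential times; median time to progression 7 months (range 5 to 10); 25% to 100% of living patients with progression still tested; a drop of 0.5 to 1.0 SD after progression, equal in both arms.

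**4. Share of scores after progression.** Death hazard = −ln(0.272)/24 = 0.0542 per month. Let S be the proportion alive and P the proportion progression-free, each summed over visits 2, 4, …, 24, and let a be the attendance after progression.

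Share = a(S − P) / [P + a(S − P)]

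- S = 6.352. For a median of 7 months P = 4.142; for 9 months P = 5.059.
- Full attendance, 7 months: 2.211/6.352 = 0.348. For medians of 5 and 10 months: 0.525 and 0.142.
- Half attendance, 7 months: 1.105/5.247 = 0.211. For 5 and 10 months: 0.356 and 0.076.

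**5. Shift in the arm contrast when the radiation effect is identical.** Shift ≈ drop × difference in share. This is a weighted-mean approximation to the mixed-model coefficient.

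| Attendance | Share, 7 months | Share, 9 months | Shift, drop 0.5 SD | Shift, drop 1.0 SD |
|---|---|---|---|---|
| 100% | 0.348 | 0.204 | 0.072 | 0.144 |
| 50% | 0.211 | 0.113 | 0.049 | 0.097 |
| 25% | 0.118 | 0.060 | 0.029 | 0.058 |

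Swapping the arms reverses the sign. For 6 versus 10 months with 50% to 100% attendance the shift is 0.10 to 0.29 SD. With progression, attendance and drop equal in both arms it is zero. With equal progression (7 months) but 25% versus 50% attendance it is (0.211 − 0.118) × 0.5 to 1.0 = about 0.05 to 0.09 SD.

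**6. A less favourable assumption for the concern.** Step 5 holds overall survival equal while progression differs, so the slower-progressing arm must have shorter survival after progression. Suppose instead that the death hazard after progression, h, is the same in both arms (assumed 0.08 to 0.12 per month) and that all deaths follow progression. With progression hazard λ = ln 2/median, the proportion alive after progression at time t is λ/(λ − h) × (e^(−ht) − e^(−λt)).

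- Example with h = 0.10 and full attendance: the shares are 3.535/7.677 = 0.461 (7 months) and 3.191/8.250 = 0.387 (9 months), a shift of 0.074 SD for a 1.0 SD drop.
- Over h = 0.08 to 0.12, attendance 50% to 100% and a drop of 0.5 to 1.0 SD: about 0.03 to 0.08 SD for 7 versus 9 months, and 0.06 to 0.15 SD for 6 versus 10. Lower attendance shrinks it further.

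**7. Against the noise.** With assumed SDs of 0.8 between and 0.6 within patients and about 5.25 scores per patient (the half-attendance total in step 4), the standard error of the arm difference at 45 per arm is √[2 × (0.64 + 0.36/5.25)/45] = 0.18 SD; at 30 per arm it is 0.22 SD. Every 7-versus-9 shift above is below one standard error.

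**The case against.** The strongest reply is that an all-scores analysis is what objective 3.2.4 asks for. The objective concerns the pattern of change over two years, is not limited to progression-free time, and fits the intention-to-treat principle in sections 11.1 and 12.3. The aim of isolating radiation appears under the primary endpoint, which handles progression. Section 12.4 also compares local and distant failure by arm, so a reader will see whether tumour control differed. Most of this stands: answering a different question from the primary is not an error. What remains is that the aim is worded for the study as a whole, that the plan does not say which question the longitudinal model answers, and that no planned version serves the stated aim.

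Three stronger readings are tempting, and the documents support none of them:
- *A reader might infer that the plan orders scores before and after progression to be pooled.* It is silent; pooling follows only from the schedule and the absence of a rule.
- *A reader might infer that the arm effect is necessarily biased.* The contrast shifts only if progression, attendance or the drop differs by arm.
- *A reader might infer that the model should simply be cut at progression and that version made the lead.* Staying progression-free is a post-randomisation state that treatment may affect. Progression under 10.2.1.3 also includes clinical deterioration and failure to return because of a worsening condition, so truncation may remove scores informatively.

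**Conclusion.** The point holds as a minor one. No longitudinal cognitive analysis in the plan separates tumour-driven from radiation-related decline, although the protocol names the second as its target. For median progression of 7 versus 9 months the arm coefficient could shift by about 0.03 to 0.14 SD in either direction; the upper half of that range depends on equal overall survival in both arms, and equal survival after progression gives 0.03 to 0.08 SD. Apart from the 27.2% survival figure and the visit schedule, every input is assumed. The effect is confined to a secondary analysis with no power claim of its own. The primary analysis, its 43 events and the sample size are not touched.

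**What to change.** In section 12.4:
- Keep the mixed model on all assessments and label it as the effect of assignment regardless of progression.
- Pre-specify a second mixed model using only assessments before progression, with progression defined and backdated as in 10.2.1.3. Report it beside the first, labelled as applying to progression-free time.
- State that the pre-progression version is the one to use when the longitudinal data are read alongside the primary result, and that it is supportive, not the sole lead.

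The cost is a few lines of text, one data filter and one extra analysis; progression dates are already needed for the primary endpoint. The restricted model has fewer observations per patient and, because it conditions on a post-randomisation event, is not a fully randomised comparison. The label should say so.

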7.0 Treatment Plan

- 7.1 Eligible patients will be randomized in equal numbers to each treatment arm using CORe. Randomization will be stratified using the following factors:7.1.1 RPA class (III or IV vs. V)
 - 7.1.2 Mini Mental Status Examination score (21-26 vs. 27-30)
 - 7.1.3 Age (less than 65 vs. 65 or older)
- 7.2 Following randomization, insurance pre-authorization will be obtained for the specified treatment modality. If a patient's insurance will not cover payment for the assigned treatment arm, that patient will be removed from the study and will be treated off protocol.
- 7.3 Radiation target definition for glioblastoma as follows. GTV defined as tumor cavity and any T1 tumor enhancement. CTV will include GTV + 2 cm margin customized to include FLAIR enhancement (if thought by the radiation oncologist to be tumor) and exclude bone, fascia, and other anatomical barriers. PTV-50 will include CTV + 3-5 mm and will be treated to 50 Gy in 30 fractions. PTV-60 boost volume will include GTV + 3-5 mm and will be treated to 60 Gy in 30 fractions.
- 7.4 For patients randomized to IMRT, treatment will be planned using Pinnacle software system. Planning will be based on non contrast CT images obtained at time of simulation in addition to MRI scan. Treatment will be delivered using linear accelerator. Fractionated radiation will be delivered daily M-F with weekends off for all patients. IMRT plans use a configuration of five to seven isocentric 6-MV photon beams delivered in a step-and-shoot technique. For inverse planning specified dose constraints are given to organs at risk including the brainstem, spinal cord, optic chiasm, optic nerves, and cochlea.

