12.0 Statistical Considerations

- 12.1 Randomization procedure: A stratified block randomization procedure will be used. Randomization will be performed using CORe. The randomization strata are as defined above in section 7.0, and the block size will be 6. Patients who withdraw from the study after randomization, but prior to receiving treatment will be considered a cancel and replaced.
- 12.2 Sample size: With IMRT the cognitive function failure rate at 4 months is 45%, based off of comparative analyses of the cognitive failure rate of RTOG 0614 and compared to the cognitive impairment seen on RTOG 0525; we hope to demonstrate that IMPT can achieve a cognitive function failure rate at 4 months of only 30%. We assume the time to cognitive failure in each treatment arm follows an exponential distribution. A cognitive failure rate of 45% at 4 months then implies a median time to cognitive failure of 4.6 months, while a cognitive failure rate of 30% at 4 months implies a median time to cognitive failure to cognitive failure of 7.8 months.

We will use a 1-sided significance level of 0.20 as suggested by Rubinstein et al. [51]for phase II screening trials. We expect to enroll 2 patients per month, and we will randomize 60 evaluable patients (30 to each treatment arm). We will have 80% power to detect an improvement in cognitive failure at 4 months from 45% in the IMRT arm to 30% in the IMPT arm. We expect to observe 43 events, and the analysis will be performed once we have observed these events. We define evaluable patients as those who have received the assigned treatment *and* completed baseline and at least one follow-up neurocognitive testing. We expect we will need an over accrual of 33% to account for those patients not evaluable. Therefore the target total enrollment sample size is 90 patients to accrue a total of 60 evaluable patients. We expect to observe 43 events, and we expect the trial to take 41 months to observe these events.

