- 12.3 Primary Analysis: The analysis will be performed on the intention-to-treat principle. Considering those patients who are not evaluable as treatment failures. We will use the methods of Gooley et al. [52]to estimate the cumulative incidence of cognitive failure in each treatment arm, considering progressive disease and death before cognitive failure as competing events. We will estimate the cumulative incidence of cognitive failure at 4 months with 95% confidence intervals. We will use the methods of Fine and Gray [53]to test for a difference between treatment arms with respect to the cumulative incidence of cognitive failure, considering progressive disease and death before and death before and death before cognitive failure as competing events. We will use the methods of Fine and Gray [53]to test for a difference between treatment arms with respect to the cumulative incidence of cognitive failure, considering progressive disease and death before cognitive failure as competing events. Our model will include treatment arm and the stratification factors used at randomization.
- 12.4 Secondary Analysis:

We will repeat the primary analysis on only those patients considered evaluable. All the secondary analyses described below will be performed using all patients as well as using only evaluable patients. We will estimate the cumulative incidence of local failure using the methods of Gooley et al. considering death as a competing event. We will model the time to local failure using the methods of Fine and Gray to test for differences between treatment arms, considering death as a competing event. Our model will include treatment arm and the stratification factors used at randomization, as well as selected dosimetric parameters. We will similarly analyze time to distant failure.

We will use the product limit estimator of Kaplan and Meier [54] to estimate overall survival stratified by treatment arm. We will also use Cox proportional hazards regression [55] to model overall survival as a function of treatment arm and the stratification factors used at randomization.

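### Section 12.4 plans no adverse-event table of irradiated patients by modality received; the two tables it does plan can each misstate toxicity, by an amount the plan leaves unknown

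*Combined protocol and SAP*

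**What the plan says.** Section 12.4 opens with a population rule: "All the secondary analyses described below will be performed using all patients as well as using only evaluable patients". It then describes local and distant failure, overall survival, quality of life and the cognitive tests, and adds: "For nearly all the prior mentioned analyses we will also plan to conduct an as-treated analysis". The next sentence is the one on safety: "We will tabulate by treatment arm the adverse events by grade and relationship to treatment". It names neither an analysis set nor a denominator.

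Section 7.1 shows that an arm is what a patient is randomised to: "Eligible patients will be randomized in equal numbers to each treatment arm using CORe". Section 12.2 defines the evaluable set by two conditions: "We define evaluable patients as those who have received the assigned treatment" and "completed baseline and at least one follow-up neurocognitive testing".

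The tables serve objective 3.2.10, a descriptive comparison of post-treatment side effects between arms. Under 10.2.10, nervous-system toxicity is recorded at each follow-up visit for two years, and only therapy-related events of grade 3 or above must be documented.

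**The concern.** The safety question is what each form of radiation does to the patients who receive it. Neither specified set answers that directly.

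- **Evaluable set.** Inclusion depends on completing at least one cognitive test after treatment. The events being counted are severe neurological ones, which can stop a patient from sitting such a test. A treated patient who is disabled or deteriorates before any follow-up test leaves the table together with the event. The plan foresees such patients: the progression definition in 10.2.1.3 includes not returning for evaluation because of death or deterioration.
- **All-patient set.** Grouping by assignment can place never-treated patients in the denominator, and can book toxicity against a modality the patient did not get.

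As-treated analyses are promised for most of the efficacy and quality-of-life work. On the order of the sentences, they stop just short of safety, where grouping by exposure matters most.

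**Working it through.** **Inputs.** From 12.2: 60 evaluable patients (30 per arm), 33% not evaluable, 90 enrolled. Assumed: 45 randomised per arm (90/2) and an even split of the non-evaluable, so 15 per arm. The plan states no adverse-event rate. The rates used in steps 4 to 6 are assumptions chosen to show a range.

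**Step 1: reproduce the plan's figure.** The plan says "We expect we will need an over accrual of 33% to account for those patients not evaluable" and "Therefore the target total enrollment sample size is 90 patients to accrue a total of 60 evaluable patients". 60/(1 − 0.33) = 89.6, which rounds up to 90, so the figure reproduces with 33% read as a share of those enrolled. Then 90 − 60 = 30 patients can be in the all-patient table and absent from the evaluable one. The plan does not split these 30 by reason.

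**Step 2: which analyses reach adverse events.** The order in 12.4 is: population rule; failure, survival, quality-of-life and cognitive analyses; as-treated sentence; adverse-event sentence. Adverse events are below the population rule, so it applies to them. They come after the as-treated sentence, which looks backwards, so literally it does not.

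**Step 3: who is in the all-patient set.**

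| Section | Patient | Handling |
|---|---|---|
| 7.2 | Insurer refuses the assigned modality after randomisation | Removed from the study, treated off protocol |
| 12.1 | Withdraws after randomisation, before treatment | Cancelled and replaced |
| 11.1 | Withdraws after randomisation, before treatment | Intention-to-treat, tracked |
| 12.3 | Not evaluable, any reason | Intention-to-treat, counted as failure |

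Under the first two rows few or no untreated patients remain. Under the last two they stay.

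**Step 4: dilution.** If u untreated patients per arm stay in the denominator, a rate is multiplied by (45 − u)/45.

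| u per arm | Factor | Assumed 20% rate reads |
|---|---|---|
| 0 | 1.00 | 20.0% |
| 5 | 0.89 | 17.8% |
| 10 | 0.78 | 15.6% |
| 15 | 0.67 | 13.3% |

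**Step 5: misattribution.** Assume true rates of 10% with IMPT and 20% with IMRT, and that c of the 45 assigned to IMPT receive IMRT. The IMPT arm then shows 0.10 × (45 − c)/45 + 0.20 × c/45. For c = 5, 10 and 15 this gives 11.1%, 12.2% and 13.3%, so the 10-point difference becomes 8.9, 7.8 and 6.7 points. For c = 0 nothing changes.

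**Step 6: exclusion from the evaluable table.** Assume 15% among the 30 evaluable patients in an arm, and k further treated patients with no follow-up test and event rate q. The rate in all treated patients is (0.15 × 30 + q × k)/(30 + k).

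| k | q = 15% | q = 30% | q = 50% |
|---|---|---|---|
| 5 | 15.0% | 6.0/35 = 17.1% | 7.0/35 = 20.0% |
| 10 | 15.0% | 7.5/40 = 18.8% | 9.5/40 = 23.8% |
| 15 | 15.0% | 9.0/45 = 20.0% | 12.0/45 = 26.7% |

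The evaluable table shows 15% in every cell. With k = 0, or with q equal to 15%, there is no distortion.

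**The case against.** The strongest reply is that there may be no bias.

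- If 7.2 and 12.1 govern, untreated patients are removed or replaced, and the dilution factor is 1.00. This stands as one possible reading, but 11.1 and 12.3 point the other way and the plan does not choose.
- No section describes on-study crossover to the other modality. Section 7.2 sends insurance refusals off protocol, and 11.2 leaves later care to the physician's judgement without mentioning the other beam. This stands, so step 5 shows only what would follow if crossover occurred.
- Section 12.4 names no denominator. Plain counts are not diluted, although crossovers would still be misattributed.
- Evaluability needs only one follow-up test, and 9.1 says the first evaluation is often about 4 weeks after radiotherapy. Severe toxicity after that test stays in the evaluable table. Patients who were never tested stay in the all-patient table, so their events are not lost from the report.
- The as-treated gap rests on sentence order, and nothing says safety was left out on purpose. That is fair, but the literal text still gives no as-treated safety table.

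A reader might go further and infer that toxicity will be diluted in one table and stripped of the sickest patients in the other, both pulling towards no difference. The documents do not support that. Non-evaluability also covers insurance refusal, withdrawal, a missing baseline test and not receiving the assigned treatment. In the evaluable set, assigned and received modality coincide, so nothing is misattributed there, and dropping patients could move the difference between arms either way. In step 5 crossover raises the IMPT arm's rate rather than lowering it.

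A reader might also infer that the annual data and safety monitoring board review inherits the problem. Section 14.3 does not say which tables or sets that review uses.

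**Conclusion.** The specification gap is established from the text: 12.4 commits to adverse-event tables by assigned arm in all patients and again in evaluable patients, and to none in irradiated patients by modality received. It is more than a missing detail, because the stated rule makes one safety table depend on cognitive testing.

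Whether bias follows, and how much, cannot be determined from the plan. The dilution factor lies between 1.00 and 0.67. The lower end needs all 30 non-evaluable patients to be untreated, evenly split by arm and kept in the denominator. The figures for misattribution and exclusion rest on assumed rates and numbers, and both effects can be zero. The point is worth correcting because the remedy is cheap and settles the safety denominator however the conflict over the all-patient set is resolved.

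**What to change.** 1. State in 12.4 that the main adverse-event table includes every patient who received at least one fraction of study radiation, grouped by the modality actually received, with that number as the denominator.
2. Keep the table by assigned arm as supportive.
3. Do not base safety conclusions on the evaluable-only table.
4. Reconcile 7.2, 11.1, 12.1 and 12.3 on who belongs to the all-patient set.

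The first three are a matter of a sentence or two and one extra grouping. The sample size and the primary test are untouched. The downside is that patients removed before any study radiation do not contribute to the main safety table. The documents do not say that adverse events are collected for patients removed under 7.2 or cancelled under 12.1, so the supportive table should report how many of its patients were assessed.
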